## **Aim**

In patients with suspected renal cell carcinoma, to evaluate radiologic features using contrast-enhanced ultrasound (CEUS), and compare them with pathologic grading at surgery.

## **Rationale**

Renal malignancies are relatively common, with lifetime risk ranging from 1 in 48 in men to 1 in 83 in women, of which renal cell carcinoma (RCC) is the most common. RCC comes in a variety of subtypes, and pathologic grade has been shown to be one factor that correlates with patient prognosis. Commonly used pathologic grading scales are the WHO / Fuhrman scales, which rely on the histologic features of the tumor, such as nuclear size, irregularity, and nucleolar prominence.

Patients with renal lesions suspicious for RCC have a variety of different treatment pathways available to them. These pathways are dependent on a number of factors, in particular size and pathologic grade. As such, radiologic surveillance with CT and MRI is common, particularly with smaller lesions. Moreover, our radiologists are being asked by urologists to biopsy more and more renal lesions to better guide their decision making. While percutaneous biopsy of renal masses is the least invasive way to obtain tissue, it still entails nontrivial cost and risk, especially that of hemorrhage given the highly vascular nature of the kidneys and renal tumors.

Contrast-enhanced ultrasound (CEUS) with Lumason contrast (Bracco) was approved for use in the USA two years ago, after many years of experience in Europe. CEUS has been shown to have the ability to differentiate renal masses from normal background renal parenchyma , with sensitivity and specificity of over 95 percent regardless of lesion size in one large study (Barr et al) It has the unique ability to be used in patients with renal dysfunction, as it is excreted by the liver and lungs. As such, it is well suited for use in patients with underlying renal pathology. It is relatively inexpensive, and the injection and use of ultrasound contrast (microbubbles) is low-risk compared with percutaneous biopsy.

Scarce literature is available regarding the utility of CEUS to help differentiate imaging findings of more aggressive RCCs versus less aggressive ones. This study will aim to use CEUS to evaluate the quantitative and qualitative imaging features of RCC prior to surgical removal, and to correlate these features with pathologic grade following surgery. We hypothesize that tumors with different pathologic grades will show different patterns of qualitative enhancement, as well as different perfusion kinetics. If findings on CEUS do correlate with pathologic grade, CEUS could possibly add additional information to the clinical decision making process, separately or in addition to biopsy at the discretion of the clinical team.

## Performance site

University Hospital

## Patient selection

### *Inclusion criteria*

1. Males and females
2. Age 18 years or greater
3. RCC suspected by referring urologist, based on clinical presentation and radiologic appearance
4. Partial or total nephrectomy planned at the performance site

### *Exclusion criteria*

1. History of acute cardiac ischemia
2. History of hypersensitivity reaction to Lumason
3. Pregnancy
4. Pathologic diagnosis at surgery is not RCC, or pathologic grading not applied to RCC
5. Renal mass unable to be visualized by grayscale ultrasound
6. Known renal vein thrombosis

## Methods

From the urologic clinic at the performance site, a urology co-investigator will identify all patients who meet inclusion criteria. The urology co-investigator will inform the patient about the study, and ascertain whether the patient is interested in participating. If so, the urology co-investigator will contact radiology research scheduling and have the patient scheduled for CEUS at the performance site, later the same day if possible. The urology co-investigator will also contact a radiology co-investigator, so that this person can consult the medical record and ensure that exclusion criteria 1-3 are not met. The patient will be given a copy of the informed consent to read prior to return for imaging.

On arrival at the ultrasound suite, a radiology co-investigator, in a room away from other patients or staff, will again describe the study, answer any questions, and seek written informed consent.

If consent is granted, the patient will undergo CEUS.

In the procedure, the patient will be imaged in the US suite at University Hospital by technicians trained in use of CEUS, under supervision of one of the study's radiologist personnel. 2.5 mL Lumason (lipid type A lyophilized powder + sulfur hexafluoride, in saline) will be injected intravenously into the antecubital fossa immediately prior to US imaging. US imaging of the kidney will then be performed, and the parameters below measured. A second injection of the same amount of contrast material may be used at the discretion of the study radiologist dependent on the quality of tumor visualization (ie. suboptimal lesion enhancement, contrast

injection malfunction, excess patient motion) with the initial dose.

Following CEUS, the lesions will be evaluated by radiology study personnel. Evaluation will consist of subjective, qualitative review of the images for pattern of enhancement, especially in relation to the normal renal cortex, which has been described as the preferred way to identify malignant renal lesions. Additional evaluation will include quantitative analysis of lesion and normal renal parenchyma perfusion dynamics using available software.

Items to be documented from the medical record, radiologic studies (CEUS and prior imaging), and surgical and pathologic records include age, sex, indication for each radiologic study, pertinent results of prior radiologic studies, time interval from RCC clinical diagnosis to surgery, CEUS quantitative findings (peak signal intensity, time to peak, area under the curve, mean transit time, of both the mass and normal renal tissue), CEUS qualitative findings (description of enhancement pattern), pertinent surgical findings, and pathologic findings including grade.

This study will monitor for adverse events (as defined below) related only to the injection of and/or physiologic reaction to Lumason. Available data shows that reactions to Lumason are rare, with the most common reactions being headache, nausea, and dizziness. True allergic reactions (ranging from hives and urticaria to anaphylactoid reactions) are even less common. Patients will be monitored by study personnel during and for at least 30 minutes after intravenous injection of contrast for immediate reactions. The patients will also be given instructions to call with any concerns in the 48 hours following contrast injection.

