#### Determining Attribution to the Investigational Procedure

Attribution: An assessment of the relationship between the AE and the study intervention. CTCAE does not define an AE as necessarily “caused by a therapeutic intervention”. After naming and grading the event, the clinical investigator must assign an attribution to the AE using the following attribution categories:

Relationship	Attribution	Description
Unrelated to investigational agent/intervention	Unrelated	The AE is clearly NOT related
	Unlikely	The AE is doubtfully related
Related to investigational agent/intervention	Possible	The AE may be related
	Probable	The AE is likely related
	Definite	The AE is clearly related

Descriptive statistics will be performed, documenting total number of patients with each item above, and comparing numbers for different pathologic grades, where pathologic grades 1 and 2

and pathologic grades 3 and 4 will be combined for inferential analysis. We will analyze how each item varies with pathologic grade using students t-test (continuous variables) and Fisher's test (categorical variables). With 40 subjects enrolled, we expect to see approximately 20 grade 1/2's and 20 grade 3/4's. At least 12 subjects per group is considered sufficient for a pilot study (ref: Julius SA. Sample size of 12 per group rule of thumb for a pilot study. *Pharmaceutical Statistics*. 2005;4(4):287–91.).

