## **Enrollment**

This is a pilot study to determine whether there is evidence that CEUS findings have correlation with pathologic staging. There has been almost no prior work done in this area and we do not have data to support sample size and power calculations. We propose imaging 40 patients because the cost of 40 Lumason doses is what we can reasonably expect to be reimbursed by our department. If we have promising results, we expect to apply for an industry or federal grant to study CEUS in a much larger population of patients with renal tumors, either at IU alone or together with other centers.

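### Does leaving open which CEUS run is analysed after a repeat injection distort the comparison by grade?

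*Combined protocol and SAP*

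**What the plan says.** The Methods section describes one injection, after which "US imaging of the kidney will then be performed, and the parameters below measured". It then allows a second, equal injection "at the discretion of the study radiologist dependent on the quality of tumor visualization (ie. suboptimal lesion enhancement"; the other two examples given are a failed injection and patient motion. All three are framed as matters of how well the tumor was visualized.

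The images are read for "pattern of enhancement, especially in relation to the normal renal cortex". The items to be documented include "CEUS quantitative findings (peak signal intensity, time to peak, area under the curve, mean transit time, of both the mass and normal renal tissue". The statistical paragraph, printed under Determining Attribution to the Investigational Procedure, combines grades 1 and 2 and grades 3 and 4, and states: "We will analyze how each item varies with pathologic grade using students t-test (continuous variables". Fisher's test is used for categorical items. About 20 patients per group are expected out of 40.

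No section says whether the first run, the second, the better one or an average is analysed. The number of injections and the reason for a repeat are not on the list of documented items. The Enrollment section calls the study a pilot and says that "we do not have data to support sample size and power calculations".

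**The concern.** One reason for a repeat lies close to the outcome. If one grade group truly enhances less, its patients will be repeated more often. If the repeat then overwrites the first reading, low values are selectively re-measured, mostly in that group. Regression to the mean lifts that group more than the other, so the observed difference in peak intensity, area under the curve or enhancement pattern shrinks.

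The Enrollment section says promising results would lead to a grant application for a much larger study. An attenuated effect estimate could therefore make that study look less worthwhile, or make it larger than it needs to be. Writing down a rule would also cost little.

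**Working it through.** **The plan's own figure.** There is no power calculation to reproduce. The 40 patients come from the budget; 40/2 = 20 per group exceeds the 12 per group cited as enough for a pilot. At 20 per group, a standardized difference has a standard error of about sqrt(1/20 + 1/20) = 0.32 SD.

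**Inputs, all assumed.** The documents give no SD, effect size, run-to-run reliability or repeat rate.
- First reading = true value + error, total variance 1, group means 0 and 0.8.
- Reliability (share of variance that is true value) 0.5, 0.7 or 0.9.
- A repeat is done if the first reading is below -1 or below -0.5. That is 16% and 4% of the two groups, or 31% and 10%: 20 × (0.16 + 0.04) = 4 patients, or 20 × (0.31 + 0.10) ≈ 8 patients.
- The second reading always replaces the first, with an upward carry-over of 0, 0.3 or 0.6 SD.
- Two-sided t-test at 0.05.

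**Standardized effect (mean difference / SD), simulated with 2,000,000 per group.** Keeping the first run gives 0.80.

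| Reliability | Repeat below | No carry-over | +0.3 SD | +0.6 SD |
|---|---|---|---|---|
| 0.5 | -1 | 0.78 | 0.76 | 0.74 |
| 0.5 | -0.5 | 0.78 | 0.75 | 0.70 |
| 0.7 | -1 | 0.79 | 0.78 | 0.76 |
| 0.7 | -0.5 | 0.79 | 0.77 | 0.74 |
| 0.9 | -1 | 0.80 | 0.80 | 0.79 |
| 0.9 | -0.5 | 0.80 | 0.79 | 0.77 |

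Without carry-over the largest loss is 0.80 - 0.78 = 0.02, and 0.02/0.32 ≈ 0.06 of a standard error. Power is 67 to 69% against 69%. A follow-up study with 80% power would need 26 to 27 per group instead of 26. The worst cell (0.70, a 12% loss) gives 58% power and 33 per group.

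The raw difference falls more than the standardized one, because the SD shrinks too: from 0.80 to 0.71-0.78 without carry-over, and to 0.58 in the worst cell.

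**What drives the loss.** At reliability 1.0 without carry-over the effect stays at 0.80. A tumor that truly enhances weakly reads weak again. The loss therefore comes from run-to-run noise or carry-over, not from biological weakness as such.

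**Failed boluses.** Suppose 5-10% of first boluses fail and lower the reading by 1.5-2.5 SD, with repeats below -1 and no carry-over. Always keeping the first run gives 0.64-0.76; using the repeat gives 0.73-0.78, and was better in 11 of 12 settings.

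**Null case.** With no true difference, the estimated difference stays within 0.002 SD of zero, and type I error is 4.7-5.2% in all 18 scenarios.

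**Enhancement pattern.** Calling readings below -0.5 weakly enhancing gives 31% against 10%, a gap of 21 points. Replacement without carry-over makes it 13-21 points, and Fisher power goes from 27% to 13-26%. The low end arises where the repeat trigger equals the cut, so that every patient counted as weak is re-measured. The odds ratio shows no consistent attenuation (4.2 against 4.0-6.1).

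**A written rule for comparison.** Take the first run unless it failed technically, judged partly on normal renal tissue. With the same bolus failures, reliability 0.5-0.7 and no carry-over, this gives 0.74-0.79 against 0.73-0.78 for the last run. Over all reliabilities without carry-over the change is about -0.01 to +0.02. With 0.6 SD carry-over at reliability 0.5-0.7 it is 0.73-0.78 against 0.66-0.74.

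**The case for a change.** The best case for acting is that the gap is real and nearly free to close. The trigger does overlap with the outcome. If the reason for a repeat is not noted at the time, a weak tumor may later be hard to tell from a failed bolus. A choice between runs made after grade is known would be an avoidable freedom; the type I error result covers only a fixed rule, and the plan does not say when images are read relative to pathology. The loss can also be larger than the standardized effect suggests. With an assumed true difference of 0.91 SD and the weakest 10-30% repeated, 2-11% of the raw difference is lost without a shift at reliability 0.5-0.9, and 17-42% if the second reading runs 1 SD higher.

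The silence on which run is analysed stands, and so does the value of noting why a repeat was done. The claim of harm is weaker. The large losses need a systematic shift for which the documents give no basis. Pattern is judged against cortex, which a shift affecting the whole bolus would raise as well. The list of documented items is introduced as what they include, so it need not be exhaustive, and the Data monitoring section has primary data captured directly from the instrument; nothing suggests that a first run would be discarded. Imaging is done on "quantitative and qualitative imaging features of RCC prior to surgical removal", so the decision to repeat is made before the surgical grade exists.

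**Conclusion.** No change to the plan follows. The text leaves the handling of repeats to the study radiologist. Since repeats are tied to image quality, the natural practice is to replace failed acquisitions and keep adequate ones. Following the plan is not shown to give a wrong or materially worse result.

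Even if the repeat always replaced the first run, the standardized effect would fall by 0-3% without carry-over, at most about 0.06 of a standard error. With failed boluses in the mix, replacement usually gains over always keeping the first run. The 12% loss needs a 0.6 SD carry-over at the lowest reliability considered. All these sizes rest on assumed effect, reliability, repeat rate and carry-over, so even the direction is uncertain. The pilot has no power target and states no figure that this would overturn. Noting at analysis which run was used and why would be good practice, but it is a detail that analysts can supply without amending the plan.

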#### Adverse Event (AE)

Any untoward medical occurrence in a patient, not necessarily having a causal relationship with the study. An adverse event (AE) can, therefore, be any unfavorable and unintended sign (including an abnormal finding), symptom, or disease temporally associated with the study, whether or not related to the study.

#### Serious Adverse Event (SAE)

A serious adverse event is any untoward medical occurrence resulting in one or more of the following:

- 1) Results in death or ANY death occurring within 28 days of date of study intervention (even if it is not felt to be study related)
- 2) Is life-threatening (defined as an event in which the patient was at risk of death at the time of the event; it does not refer to an event which hypothetically might have caused death if it were more severe)
- 3) Requires inpatient hospitalization  $\geq$  24 hours or prolongation of existing hospitalization
  - **NOTE:** Hospitalizations that are not considered SAEs are:
    - Hospitalization planned prior to first study intervention

- Hospitalization less than 24 hours
- Hospitalization for elective treatment of a pre-existing condition unrelated to the study intervention

- 4) Results in persistent or significant disability/incapacity
- 5) Is a congenital anomaly or birth defect
- 6) Is an important medical event (defined as a medical event(s) that may not be immediately life-threatening or result in death or hospitalization but, based upon appropriate medical and scientific judgment, may jeopardize the patient or may require intervention (e.g., medical, surgical) to prevent one of the other serious outcomes listed in the definition above). Examples of such events include, but are not limited to, intensive treatment in an emergency room or at home for allergic bronchospasm; blood dyscrasias or convulsions not resulting in hospitalization; or the development of drug dependency or drug abuse.

#### Unexpected Adverse Event

An adverse event not associated as a known risk or adverse event.

#### Determining Attribution to the Investigational Procedure

Attribution: An assessment of the relationship between the AE and the study intervention. CTCAE does not define an AE as necessarily “caused by a therapeutic intervention”. After naming and grading the event, the clinical investigator must assign an attribution to the AE using the following attribution categories:

Relationship	Attribution	Description
Unrelated to investigational agent/intervention	Unrelated	The AE is clearly NOT related
	Unlikely	The AE is doubtfully related
Related to investigational agent/intervention	Possible	The AE may be related
	Probable	The AE is likely related
	Definite	The AE is clearly related

Descriptive statistics will be performed, documenting total number of patients with each item above, and comparing numbers for different pathologic grades, where pathologic grades 1 and 2

and pathologic grades 3 and 4 will be combined for inferential analysis. We will analyze how each item varies with pathologic grade using students t-test (continuous variables) and Fisher's test (categorical variables). With 40 subjects enrolled, we expect to see approximately 20 grade 1/2's and 20 grade 3/4's. At least 12 subjects per group is considered sufficient for a pilot study (ref: Julius SA. Sample size of 12 per group rule of thumb for a pilot study. *Pharmaceutical Statistics*. 2005;4(4):287–91.).

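### Continuous items are compared by grade with Student's t-test although the grade groups may be uneven; Welch's version would cost almost nothing (low priority)

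*Combined protocol and SAP*

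**What the plan says.** The statistical paragraph stands at the end of the section Determining Attribution to the Investigational Procedure. It combines grades 1 and 2, and grades 3 and 4, and then states: "We will analyze how each item varies with pathologic grade using students t-test (continuous variables) and Fisher's test (categorical variables". It does not mention unequal variances, a significance level or confidence intervals.

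On group sizes, with 40 enrolled, the same paragraph says "we expect to see approximately 20 grade 1/2's and 20 grade 3/4's", and adds: "At least 12 subjects per group is considered sufficient for a pilot study". Item 4 of the Exclusion criteria removes patients on a finding available only after the scan: "Pathologic diagnosis at surgery is not RCC, or pathologic grading not applied to RCC".

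The continuous items include four perfusion parameters: peak signal intensity, time to peak, area under the curve and "mean transit time, of both the mass and normal renal tissue". They bear on the Rationale's hypothesis that grades differ in enhancement pattern "as well as different perfusion kinetics". The Enrollment section calls the study a pilot, says there are no data for power calculations, and says promising results would lead to a grant application for a larger study.

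**The concern.** Student's t-test pools the two group variances. With equal group sizes, pooling gives the right standard error on average even if the spreads differ. With unequal sizes it does not. If the smaller group is the more variable, the standard error is too small and the test rejects too often. If the larger group is the more variable, the reverse happens.

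Nothing in the design fixes the split. Patients are imaged first and graded later, and those without a graded RCC drop out. Losing patients does not by itself disturb the test; an uneven split combined with unequal spreads does. What is at stake is modest: whether the p-values and intervals that help decide if the results are promising mean what they appear to mean.

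**Working it through.** **Inputs.** From the documents: 40 patients, an expected split of about 20/20, and a rule-of-thumb minimum of 12 per group. Assumed, because the documents give none of them: two-sided 5% level, normal data, SD ratios of 1.5:1 and 2:1, and a difference of 0.8 SD for power. The plan has no power or precision figure to reproduce; 20 + 20 = 40 is consistent.

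**1. How uneven could the split be?** If each of 40 graded patients is equally likely to fall in either group, the number in one group is Binomial(40, 0.5).
- 16/24 or more uneven: 2 × P(X ≤ 16) = 0.27.
- 12/28 or more uneven: 2 × P(X ≤ 12) = 0.02.

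If the true grade mix is not even, uneven splits become more likely.

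**2. Where the distortion comes from.** The true variance of the difference in means is V = σ₁²/n₁ + σ₂²/n₂. Student's test on average uses S = s_p² × (1/n₁ + 1/n₂), with s_p² = [(n₁−1)σ₁² + (n₂−1)σ₂²]/(n₁+n₂−2).

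Example, 16/24, with SD 1.5 in the smaller group and 1 in the larger:
- V = 2.25/16 + 1/24 = 0.1823
- s_p² = (15 × 2.25 + 23 × 1)/38 = 1.4934
- S = 1.4934 × (1/16 + 1/24) = 0.1556
- V/S = 1.17, square root 1.08
- The critical value 2.024 (38 df) acts like 2.024/1.0825 = 1.870, and 2 × P(t₃₈ > 1.870) = 6.9%.

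At n₁ = n₂ = n, V and S both equal (σ₁² + σ₂²)/n, so the ratio is exactly 1.

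**3. Type I error.** The approximation is the one in step 2. The last two columns are simulated; repeat runs agree within a few tenths of a point.

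| Split | More variable group | SD ratio | V/S | Student's, approx. | Student's, simulated | Welch, simulated |
|---|---|---|---|---|---|---|
| 16/24 | smaller | 1.5:1 | 1.17 | 6.9% | 7.0% | 5.0% |
| 16/24 | larger | 1.5:1 | 0.85 | 3.5% | 3.5% | 5.0% |
| 16/24 | smaller | 2:1 | 1.28 | 8.2% | 8.4% | 5.1% |
| 16/24 | larger | 2:1 | 0.78 | 2.8% | 2.9% | 5.0% |
| 12/28 | smaller | 2:1 | 1.66 | 12.4% | 12.6% | 5.1% |
| 12/28 | larger | 2:1 | 0.61 | 1.3% | 1.4% | 4.9% |
| 20/20 | either | 2:1 | 1.00 | 5.0% | 5.3% | 5.1% |

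**4. Averaged over splits.** Weighting every split by its Binomial(40, 0.5) probability gives Student's an overall type I error of about 5.2% (SDs 1.5:1) to 5.5% (2:1). The two directions largely cancel, and most of the probability lies near 20/20.

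**5. Price of Welch when SDs are equal.** Simulated power at a 0.8 SD difference is 69.0% (Student's) against 68.9% (Welch) at 20/20, and 62.0% against 60.1% at 12/28.

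**The case against.** The strongest case against raising this is that it seldom matters. The plan expects about 20/20, where the tests hardly differ. The larger distortions need an uneven split and unequal spreads together, and the inflation also needs the smaller group to be the more variable. The 12/28 case has about a 2% chance under even odds, and averaged over splits Student's stays at 5.2–5.5%. This is a pilot with no stated significance threshold. All of that stands, and it is why the priority is low. But the trial will be analysed at the split it gets, not at an average, and the protection costs almost nothing.

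A reader might infer something stronger from the Methods section. It plans "quantitative analysis of lesion and normal renal parenchyma perfusion dynamics using available software", yet no section says how a patient's mass and normal-tissue values are used together in the quantitative analysis. One could conclude that the plan is deficient without a model adjusting the mass value for the normal-tissue value. The documents do not support that conclusion:
- The plan to test each item already covers a grade comparison of the normal-tissue values.
- Any gain depends on a within-group correlation that the documents do not give. At 20/20 and 0.8 SD, simulated power is 69% unadjusted. Adjusted, it is 68%, 72%, 80% and 93% at assumed correlations of 0, 0.3, 0.5 and 0.7. There is no gain below about 0.16.
- Grade groups are not randomised, so adjustment can change the quantity estimated. If normal tissue shifts by 0.3 SD in the same direction as the mass, a true 0.8 SD becomes 0.8 − 0.3 × correlation: 0.71, 0.65 or 0.59 SD at correlations of 0.3, 0.5 and 0.7. With no mass difference, that shift makes the adjusted test reject in 6%, 8% or 14%.
- An ordinary linear model keeps the equal-spread assumption: 12.7% type I error at 12/28 with SDs 2:1 and correlation 0.5.

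**Conclusion.** The point holds as a cheap, low-priority improvement. Student's t-test is a usable choice for this pilot and is close to nominal at the expected split. It is miscalibrated only when the split is uneven and the spreads differ, by amounts running from about 7% or 3% (16/24, SDs 1.5:1) to about 12.6% or 1.4% (12/28, SDs 2:1) in place of 5%. Welch's test stays near 5% throughout.

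The arithmetic is secure; whether the trial will meet those conditions is unknown, because the SD ratios, the level and the even-odds model for the split are all assumptions. Two inferences go too far: that the planned analysis is invalid, and that the plan must link mass and normal-tissue values in an adjusted model. Welch protects the error rate; it does not improve precision.

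**What to change.** In the statistical paragraph, replace Student's t-test with Welch's (unequal-variance) t-test for continuous items, and report each difference between grade groups with its 95% confidence interval. Fisher's test for categorical items is unaffected. This is a wording change that needs no new data; its price is the power given in step 5 of the working, under 1 point at 20/20 and about 2 at 12/28 when SDs are equal.

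Optionally, report the within-group correlation between mass and normal-tissue values for each of the four perfusion parameters, as a descriptive input for planning the larger study. Both values should come from the same injection. The Methods section says "A second injection of the same amount of contrast material may be used at the discretion of the study radiologist", and its list of items does not include which injection supplied each value, so that would need recording.

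A model adjusting the mass value for the normal-tissue value is not part of this change. If the investigators want one, it should be labelled exploratory and shown beside the unadjusted result, not in its place.

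### Every recorded item is tested against grade group, but no between-group difference with an interval, measure of separation or lead measure is planned; a cheap, minor improvement for a pilot of about 20 v 20

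*Combined protocol and SAP*

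**What the plan says.** The whole statistical plan is one paragraph at the end of the section Determining Attribution to the Investigational Procedure. It provides for descriptive statistics by pathologic grade, then pools grades 1 and 2 and grades 3 and 4 for what it calls inferential analysis: "We will analyze how each item varies with pathologic grade", with Student's t-test for continuous items and Fisher's test for categorical ones. It expects 40 subjects to divide into about 20 and 20, and cites a rule of thumb of 12 per group for pilots.

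The items are listed in Methods. They include "CEUS quantitative findings (peak signal intensity, time to peak, area under the curve, mean transit time, of both the mass and normal renal tissue"), the enhancement pattern, and also age, sex, indication, prior imaging results, time to surgery and surgical findings. Counting the eight perfusion measures separately gives about 15 items.

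The hypothesis in the Rationale is that "tumors with different pathologic grades will show different patterns of qualitative enhancement, as well as different perfusion kinetics". The gap in the literature described there is whether CEUS can help "differentiate imaging findings of more aggressive RCCs versus less aggressive ones".

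Enrollment calls the study a pilot "to determine whether there is evidence that CEUS findings have correlation with pathologic staging", says that "we do not have data to support sample size and power calculations", and gives the next step: "If we have promising results, we expect to apply for an industry or federal grant".

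Nowhere does the plan name a significance level, a between-group difference, an interval, a measure of discrimination, a lead measure, or a rule for reading the p-values.

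**The concern.** A pilot that starts without data for a power calculation is the natural source of planning figures for the larger study. That study will need estimates of how far the grade groups differ and how uncertain those estimates are. The inferential output planned here is a set of tests, which supplies neither. Nor does a test say how well CEUS separates more from less aggressive tumors, which is the use described in the Rationale.

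At this size, p-values alone are easily misread in both directions. A non-significant result says little about whether a moderate difference exists. A significant one tends to come with an inflated estimate. With several measures and no lead, one significant result may also arise by chance. What is at stake is how well the pilot informs the decision to seek a larger study. The documents tie no treatment decision to these p-values.

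**Working it through.** **Inputs from the documents.** 40 enrolled, about 20 v 20; a floor of 12 per group (statistical paragraph). Four perfusion parameters in each of mass and normal tissue, so 8 measures (Methods). The 40 are patients imaged (Enrollment), and Exclusion criterion 4 later removes those for whom "Pathologic diagnosis at surgery is not RCC, or pathologic grading not applied to RCC". The loss rate is not stated, so 17 v 17 and 12 v 12 are shown as illustrations.

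**Assumptions not in the documents.** Two-sided 0.05; equal groups; normal data; true differences of 0.5 SD, with 0.6 and 0.8 SD as a range.

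**The plan's own figure.** 20 + 20 = 40. There is no power calculation to reproduce.

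**Power.** Noncentral t with 2n − 2 df and noncentrality d × √(n/2). For d = 0.5, n = 20: 0.5 × √10 = 1.58, critical t = 2.024.

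**Half-width of the 95% CI for a mean difference (SD units).** t(0.975, 2n − 2) × √(2/n). For n = 20: 2.024 × √0.1 = 0.64.

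**Average overstatement.** Mean absolute observed difference among simulated results with p < 0.05, divided by the true difference.

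| Per group | Power at 0.5 SD | Difference detectable with 80% power | CI half-width | Mean significant estimate if true 0.5 SD | Ratio at 0.5 SD | Ratio at 0.8 SD |
|---|---|---|---|---|---|---|
| 20 | 34% | 0.91 SD | 0.64 SD | 0.83 SD | 1.67 | 1.20 |
| 17 | 29% | 0.99 SD | 0.70 SD | 0.89 SD | 1.78 | 1.26 |
| 12 | 22% | 1.20 SD | 0.85 SD | 1.03 SD | 2.06 | 1.42 |

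At 20 v 20 the half-width of 0.64 SD exceeds 0.5 SD, so even an observed difference of zero is compatible with a true difference of 0.5 SD in either direction.

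The ratios are averages. At 20 v 20 and 0.5 SD the median is about 1.6, and about 40% of significant results reach 1.7. At 0.6 SD the mean ratio is 1.45.

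**Chance of at least one false positive**, if any significant measure counted as evidence. For four independent mass parameters: 1 − 0.95⁴ = 18.5%. Simulated at 20 v 20 with equal correlation: 16% at 0.5, 13% at 0.7, 9% at 0.9. The range is practically the same at 17 v 17 and 12 v 12. If the four normal-tissue measures also counted: 1 − 0.95⁸ = 34% if independent, falling to 12% at correlation 0.9.

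**ROC area.** Hanley–McNeil standard error at area A = 0.75: Q₁ = A/(2 − A) = 0.600; Q₂ = 2A²/(1 + A) = 0.643; SE² = [A(1 − A) + (n − 1)(Q₁ − A²) + (n − 1)(Q₂ − A²)]/n². At n = 20, SE = 0.078 and the half-width is 1.96 × 0.078 = 0.15. It is 0.17 at 17 v 17 and 0.20 at 12 v 12.

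**Difference in proportions.** At 50% v 50% and 20 v 20: 1.96 × √(2 × 0.25/20) = 0.31, or 31 percentage points.

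**The case against.** The strongest reply is that the framing is largely right already. Enrollment calls the study a pilot, concedes that there are no data for power, and names a larger study as the next step. Descriptive summaries by grade are planned. The word inferential appears once, to explain the pooling of grades, and makes no confirmatory claim. All of this stands, and it is why the point is minor.

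Several stronger readings are tempting, and the documents do not support them.

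- *That significant results would be inflated at least 1.7-fold.* The figure is a mean under an assumed 0.5 SD and 20 v 20. Most significant results in that setting fall below it, and larger true differences lower it.
- *That p < 0.05 defines a promising result, or that a null test will be read as no effect.* No section says either.
- *That the next study will be sized on an inflated estimate.* Sizing on 0.83 SD would give 24 per group instead of 64, with 40% power for 0.5 SD, but nothing in the plan proposes this.
- *That multiplicity adjustment is required.* In a pilot of this kind it is not. The false-positive figures only show why a single significant measure deserves little weight.
- *That the normal-tissue measures are surplus.* Methods reads enhancement in relation to normal cortex, so they may be a deliberate reference.

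It is also fair to say that estimates do not remove selection. If four measures all truly differed by 0.5 SD at 20 v 20, choosing the largest estimate would overstate it about 1.65-fold if independent and about 1.5-fold at correlation 0.5. The fix has to allow for this.

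What remains is that pilot status explains the small sample but does not supply the missing estimates and intervals. It is the main reason for wanting them.

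**Conclusion.** The concern holds as a minor point of analysis and reporting. The plan tests every recorded item against grade group and commits to no difference with an interval, no measure of separation and no lead measures, in a study whose value lies in informing a larger one.

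Under two-sided 0.05 and a true 0.5 SD difference, both assumed, power is 34% at 20 v 20 and 22% at 12 v 12. Average overstatement among significant results is about 1.7-fold and 2.1-fold, or about 1.2-fold and 1.4-fold if the true difference is 0.8 SD. If any significant mass parameter were taken as evidence, which the plan does not say, the chance of at least one false positive would be about 9% to 19%, depending on correlation. The omissions can be read directly from the text; the sizes depend on the assumed effect and the number of evaluable patients.

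**What to change.** In the statistical paragraph:

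- For each quantitative CEUS measure, report the between-group difference and the ROC area for grade 3/4 v 1/2, each with a 95% CI.
- For enhancement pattern, report the difference in proportions (or the odds ratio) with a 95% CI.
- Name the four mass parameters and enhancement pattern as the lead measures, and report the normal-tissue measures as reference.
- Label any p-values exploratory and unadjusted.
- Summarise the non-CEUS items by grade group without tests.

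In Enrollment, say that whether results are promising will be judged on all lead estimates and their intervals together, and note that picking out the largest estimate also overstates the effect. Record this in a dated note before CEUS is first compared with grade; Data monitoring plans quarterly extraction of analysis data, so the note should come early.

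Cost: no extra patients, scans or visits, and a little more analysis. The drawback is less weight on any single significant result, and intervals that will be visibly wide: at 20 v 20, about ±0.64 SD for a mean difference and ±0.15 for an ROC area of 0.75.
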